Is the perfusion index an accurate predictor of return of spontaneous circulation in cardiac arrest?

NCT: pending

STUDY SUMMARY

Title

Is the perfusion index an accurate predictor of return of spontaneous circulation in cardiac arrest?

Methodology

A perspective observational double blind study

Outcomes

Return of spontaneous circulation in a mixed population of out-of-hospital and in-hospital cardiac arrest

Study Duration

Estimated duration for the main protocol (e.g. from start of screening to last subject processed and finishing the study) is approximately 2.5 years

Study Center

Monocentric: Centre Hospitalier Universitaire Saint Pierre, Brussels, Belgium

Objectives

Primary Objective: To evaluate the sensibility and specificity of the perfusion index in predicting further return to spontaneous circulation

Secondary Objectives: To compare perfusion index specificity and sensibility in predicting further return to spontaneous circulation compared to end-tidal CO₂

Number of Subjects

92 non-randomized patients in one arms

Main Inclusion Criteria

Inclusion Criteria

- Male and female patients, 12-99 years old, in any distribution.
- Cardiac arrest with an indication to reanimate
- Consent and compliance with all aspects of the study protocol, methods, providing data during the cardiac arrest management

Exclusion Criteria

- Male and female patients younger than 12 years old or older than 99 years old.
- Prisoners
- Pregnant women

Study parameter

- Perfusion index during cardiac arrest

Statistical

Methodology

Primary Endpoint:

Sensibility and specificity of the perfusion index in predicting a return of spontaneous circulation (ROSC)

Secondary Endpoints:

Comparison of receiver operator curves from the perfusion index and the end-tidal CO₂ in predicting ROSC

Determination of the receiver operating characteristic curve of an index combining perfusion index with ETCO₂ and current rhythm

Tertiary Endpoints:

Sensibility and specificity of the perfusion index in predicting further arrest following an initial ROSC

Purpose:

The primary objective is to evaluate the sensibility and specificity of the perfusion index, measured during chest compressions for cardiac arrest, in predicting ROSC.

Background:

Cardiac arrest prognostication is important in to inform the decision to cease resuscitation or, in the prehospital setting, to inform the decision on transport to hospital. Currently the only intra-arrest monitoring tools widely available with proven prognostic value are the underlying cardiac rhythm identified on electrocardiogram and end-tidal CO₂ (ETCO₂) measurement. Shockable rhythms, namely ventricular fibrillation and pulseless ventricular tachycardia, are associated with better outcomes than non-shockable rhythms such as pulseless electrical activity and asystole.

ETCO₂, so far, is considered the best tool available for prognostication during in or out-of-hospital cardiac arrest. Previous studies have examined ETCO₂ readings and trends at various times during cardiac arrest as a possible predictor of ROSC, survival to admission, and survival to hospital discharge. Nonetheless, ETCO₂ values have numerous limitations and no value alone can safely and accurately predict the chances of return to a spontaneous circulation (ROSC) or can safely inform on the futility of further reanimation. It would be therefore interesting for the clinician on the ground to be able to rely on a panel of different parameters to assess the chances of ROSC in a multimodal way.

Goals of the study:

1. To examine the association between absolute values of the perfusion index during resuscitation and ROSC.
2. To examine the association between the change in perfusion index values during resuscitation and ROSC.
3. To compare the performance of the perfusion index to ETCO₂ in predicting the chances of ROSC.
4. To study a combined index including rhythm, ETCO₂ and perfusion index achieves in predicting ROSC.
5. To study the ability of perfusion index to predict further arrests in patients further re-arrests in patients that achieved an initial ROSC

Duration of the Study:

The study is estimated to complete enrollment within 12 months from study initiation; however, enrolment will remain open until the study goal is met. The duration of this study for each subject will be a maximum of two years.

Product Description:

Perfusion index will be measured a the finger tip using a Radical 97 monitor (Masimo, Irvine, California). Masimo Signal Extraction Technology (SET[®]) pulse oximetry yields continual and simultaneous absolute values and trends.

Perfusion index (PI) is an assessment of the pulsatile strength at a specific monitoring site, and as such PI is an indirect and noninvasive measure of peripheral perfusion. It is calculated by means of pulse oximetry by expressing the pulsatile signal as a percentage of the nonpulsatile signal, both of which are derived from the amount of infrared (940 nm) light absorbed. The PI value is relative to a particular monitoring site, (e.g. the fingertip or toe), of each patient as physiological conditions vary between monitoring sites and individual patients.

Potential Benefits and Risks to Patients:

No foreseeable benefit can be expected on included patients.

Given the observational design and the well studied effects of continuous non-invasive infrared pulse oximetry monitoring we can reliably declare that we expect no possible harm to the patients included in the study.

Methods:

Study Design.

Double-blind study involving ninety two subjects treated with advanced life support according to the European Resuscitation Council (ERC) recommendations will be included in one observatory arms. Patient treatment during resuscitation will be determined by the treating clinician within the frame of ERC recommendations. Monitoring of perfusion index will be initiated as soon as possible and recorded until the end of the resuscitation efforts. ETCO₂ will be placed as soon as possible and recorded until the end of the resuscitation irrespectively if measured while the patient is ventilated through a bag-valve-mask or through a advanced infraglottic airway.

Study population and selection criteria.

All aspects of the study and consent forms will be approved by our Ethical Board prior to implementation. All patients in cardiac arrest, after application of the inclusion and exclusion criteria, with an indication to initiate an advanced life support will be included in the study. Included participants that will be successfully reanimated and that will regain a sufficient level of consciousness will be required to sign a full informed consent.

Inclusion criteria will be a cardiac arrest in a subject aged between 12 to 99 years old with an indication to start an ALS.

Subjects will be excluded from the study if younger than 12 years old, if pregnant or if prisoners at study inclusion.

We aim to recruit 90 patients in cardiac arrest for whom an ALS has been initiated.

Recruitment methods.

All subjects that will be treated by the mobile intensive care unit of CHU Saint Pierre during study period will be screened for eligibility. Subjects having regained a sufficient neurological awareness to sign an informed consent for the study will review and undergo informed consent.

This study will be listed at www.clinicaltrials.gov.

Data collection and reporting.

Data will be collected throughout the intervention up until death or hospital admission or intensive care admission whichever comes first.

Expected outcomes.

It is the sponsor's expectation that higher perfusion index and upwards trends will be associated with higher chances of ROSC during ALS. Moreover, the sponsor expectation is that lower perfusion index following ROSC will be associated with higher chances of re-arrest. Finally the sponsor expect that a combined index including PI, ETCO₂ and rhythm would overperform each of these items in terms of capacity of predicting ROSC chances.

Adverse reactions.

There is no expectation of any adverse outcomes or reactions due to a patient being monitored with a Radical 97 monitor. Any adverse reactions should be reported immediately to the principal investigator or co-investigators

Reasons for Withdrawal or Termination

A subject may be discontinued from the study at any time if the subject, the Investigator, or the Sponsor feels that it is not in the subject's best interest to continue.

The following is a list of possible reasons for study treatment discontinuation:

- Screening Failure
- Subject withdrawal of consent
- The treating clinician is not compliant with study or ERC procedures
- Adverse Event that in the opinion of the Investigator would be in the best interest of the subject to discontinue study participation
- Protocol violation requiring discontinuation
- Mechanical – technical failure of the monitor

Handling of Participant Withdrawals of Termination:

Although subjects may withdraw from the study at any time and for any reason, (or may be withdrawn according to the abovementioned pre-specified cases), subject withdrawal should be avoided as much as reasonably possible.

Premature Termination or Suspension of Study:

This study may be temporarily suspended or prematurely terminated if there is sufficient reasonable cause. Written notification, documenting the reason for study suspension or termination, will be provided by the suspending or terminating party to the Investigator, and the Sponsor.

SAMPLE SIZE JUSTIFICATION

Sample Size Calculations

We an expected sensitivity and specificity of 90% for PI to predict ROSC, an expected prevalence of ROSC of 40%, a precision of 10% and a type I error rate of 0.05 we calculated a required sample size of 87. Including a possible dropout of 5% we calculated a final sample size of 92.

STATISTICAL ANALYSIS PLAN

Primary Endpoint

We will determine the predictive value of PI measures for ROSC. We will calculate the sensitivity and specificity at multiple different PI thresholds along with corresponding 95% confidence intervals. Overall discrimination of PI for ROSC will be presented as area under the receiver operator characteristic curve (AUC/ROC). PI values will be averaged on two minutes. Each value will be tested for its ability to predict ROSC during the following ALS cycle (2 minutes). To assess the trending ability of PI to detect ROSC we will measure the difference (ΔPI) between initial PI and PI values of the cycle preceding ROSC or the last cycle in the absence of ROSC. We will then examine the association between ΔPI and ROSC through a multivariable logistic regression while adjusting for predetermined baseline confounders such as age, initial rhythm, noflow time, bystander CPR and sex.

Secondary Endpoints

Superiority analysis of PI compared to ETCO₂ in predicting ROSC. Initial and final values of both PI and ETCO₂ will be assessed for their ability to predict ROSC. Moreover averaged values per 2 min cycle will be assessed for their ability to predict ROSC in the following cycle. The constructed ROC curves will be compared using the algorithm suggested by De Long.

Tertiary Endpoints

As a tertiary endpoint we will study the predictive value of PI to predict further re-arrest following a ROSC. Overall discrimination of PI for re-arrest will be presented as area under the receiver operator characteristic curve (AUC/ROC). PI values will be averaged on two minutes. Each value will be tested for its ability to predict a re-arrest during the following 2 minutes.

ASSESSMENT OF SAFETY

Adverse events (AE) will be monitored and collected by the study team during the monitoring phase of the study. For each AE, a detailed explanation will be obtained from the treating physician and medical record. All AEs will be recorded on the CRFs.

Definition of Adverse Event

An AE is defined as any unanticipated medical occurrence regardless to relationship of the investigative arm of the trial. An AE can be any unintended sign symptom, or disease associated with the trial

Definition of Serious Adverse Event

An adverse event is considered serious if it results in any of the following:

1. Death
2. A life-threatening AE
3. Prolong existing hospitalization
4. Persistent disability/incapacity
5. Medically important event by the Investigator

Severity of Event

The Investigator will be asked to assess the severity of the AE using the following categories:

Mild: Events require minimal or no treatment and do not interfere with the participant's daily activities.

Moderate: Events result in a low level of inconvenience or concern with the therapeutic measures. Moderate events may cause some interference with functioning.

Severe: Severe events are usually potentially life-threatening or incapacitating.

Relationship to Study Products

For all collected AEs, the clinician who examines and evaluates the participant will determine the AE's causality based on temporal relationship and his/her clinical judgment. The degree of certainty about causality will be graded using the categories below.

Definitely: The relationship of the AE and the study device or the study procedure can definitely be established.

Probably: While a clear relationship to the study device or to the study procedure cannot be established, the AE is associated with an expected AE or there is no other medical condition or intervention, which could explain the occurrence of such an event.

Possibly: There is no clear relationship between the AE and the study device or study procedure; however, one cannot definitely conclude that there is no relationship.

Unrelated: There is no relationship between the AE and the study device or study procedure. This may include but is not limited to the incident being an expected outcome of a previously existing or concurrent disease, concomitant medication or procedure the subject experienced.

SAE Reporting

In the case of a SAE, the Investigator must notify the Sponsor within 1 working day after the Investigator first learns of the event.

Data Safety Monitoring

As the monitor technique implemented in the study are currently being used as standard of care, the study team does not anticipate subjects experiencing any adverse events solely due to being in the study. Therefore, a formal Data Safety Monitoring Board will not be needed for this study.

DATA MONITORING

The Principal Investigator will be responsible to ensure the study is conducted in accordance with the protocol, Good Clinical Practice (GCP), applicable regulatory requirements, and that the data recorded is valid. To achieve this objective, the study will be continuously monitored and reviewed on a two-month basis by the study team. Clinical site monitoring is conducted to ensure that the rights and well-being of human subjects are protected, that the reported trial data are accurate, complete, and verifiable, and that the conduct of the trial is in compliance with the currently approved protocol/amendment(s), with GCP, and with applicable regulatory requirement(s).

A Clinical Monitoring Plan will be created by the Sponsor and describe in detail who will conduct the monitoring, at what frequency monitoring will be done, at what level of detail monitoring will be performed, and the distribution of monitoring reports.

DATA HANDLING AND RECORD KEEPING

The collection of personal patient information will be limited to the amount necessary to achieve the aims of the research, so that no unneeded sensitive information is being collected. Only study

personnel will collect data. Hard copy documents will be retained for the duration of the study until data entry. All hard copy documents will be kept in a locked cabinet in the nurse research coordinator's office. Data will be exported into Excel format (password protected), which will then be used for data analysis. Only de-identified data will be used for data analysis. All hard copy documents will be shredded within ten years after completion of the study upon Sponsor approval. Collected de-identified data will be sent to a biostatistician for statistical analysis.

INSTITUTIONAL ETHICAL REVIEW BOARD

The protocol, informed consent form(s), and all participant materials will be submitted to the Ethical Board for review and approval. Approval of both the protocol and the consent form must be obtained before any participant is enrolled. Any amendment to the protocol will require review and approval by the Ethical Board before the changes are implemented to the study. All changes to the consent form will be approved by the Ethical Board; a determination will be made regarding whether previously consented participants need to be re-consented.

PUBLICATION AND DATA SHARING POLICY

The preparation and submittal for publication of manuscripts containing the study results shall be in accordance with a process determined by mutual written agreement among the study Sponsor and participating institutions. The publication or presentation of any study results shall comply with all applicable privacy laws, including, but not limited to, the Health Insurance Portability and Accountability Act of 1996.

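### The recruitment aim of 90 contradicts the sample size of 92 given elsewhere in the protocol; after the planned 5% dropout, 90 leaves 85.5 patients against the 87 required

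*Protocol*

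**What the plan says.** The protocol states the patient total in four places.

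- Study Summary, Number of Subjects: "92 non-randomized patients in one arms".
- Methods, Study Design: "Double-blind study involving ninety two subjects treated with advanced life support".
- Methods, Study population and selection criteria: "We aim to recruit 90 patients in cardiac arrest for whom an ALS has been initiated".
- Sample Size Calculations: "we calculated a required sample size of 87", followed by "Including a possible dropout of 5% we calculated a final sample size of 92".

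Three of the four totals are 92 and one is 90. The last place is the only one that derives its figure. Its inputs are an "expected sensitivity and specificity of 90% for PI to predict ROSC", "an expected prevalence of ROSC of 40" per cent, a precision of 10% and a type I error rate of 0.05.

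On when recruitment ends, Duration of the Study says that "enrolment will remain open until the study goal is met".

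**The concern.** Two different recruitment totals stand a few paragraphs apart in the Methods section, with nothing to reconcile them. The lower one is in the section that defines who is to be recruited, and it is given as an exact number.

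Two things are at stake. First, enrolment has no fixed closing date, so the total is the natural stopping point. A reader of the study population section could close at 90, while a reader of the summary or the sample size section would continue to 92. Second, if 90 were followed, the dropout allowance built into the calculation would be partly lost, and the expected evaluable number would fall below what the protocol says it needs.

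**Working it through.** **Inputs, all from Sample Size Calculations.** Sensitivity and specificity 0.90 each, ROSC prevalence 0.40, precision 0.10, type I error 0.05, dropout 5%. Two readings are assumed because the text does not spell them out: precision is the half-width of the confidence interval, and the error rate is two-sided (z = 1.96). These readings reproduce the protocol's figure.

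**Reproducing 87.** The number of ROSC patients needed for sensitivity is z² × Se × (1 − Se) / d²:

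- 1.96² × 0.90 × 0.10 / 0.10² = 34.57
- Total patients for sensitivity: 34.57 / 0.40 = 86.4, rounded up to **87**
- Total patients for specificity: 34.57 / 0.60 = 57.6, rounded up to 58

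Sensitivity governs, and 87 agrees with the protocol.

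**Reproducing 92.** Both usual ways of adding 5% give the same answer:

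- 87 / 0.95 = 91.58, rounded up to **92**
- 87 × 1.05 = 91.35, rounded up to **92**

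The protocol's calculation is therefore sound. The figure of 90 is neither the number before dropout nor the number after it.

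**What 90 delivers on the protocol's own assumptions.** Evaluable patients are N × 0.95, ROSC patients are 40% of those, the half-width is 1.96 × √(0.09 / ROSC patients), and the tolerable dropout is 1 − 87/N.

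| | 90 recruited | 92 recruited |
|---|---|---|
| Evaluable at 5% dropout | 85.5 | 87.4 |
| Difference from 87 | −1.5 | +0.4 |
| Expected ROSC patients | 34.2 | 34.96 |
| Half-width for sensitivity (percentage points) | 10.05 | 9.94 |
| Largest dropout that still leaves 87 | 3.3% | 5.4% |

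Against the unrounded requirement of 86.44, the shortfall with 90 is 86.44 − 85.5 = 0.94 patient.

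**Scale.** The expected difference in ROSC patients is 2 × 0.95 × 0.40 = 0.76. The chance variation in the ROSC count among 87 patients has a standard deviation of √(87 × 0.4 × 0.6) = 4.57, about six times as large.

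**The case against.** The strongest reply is that the discrepancy has almost no consequence. Half-widths of 10.05 and 9.94 points both round to the stated 10%. The 5% is described as a possible dropout, so it is an allowance and not a known rate. The intended figure is also easy to identify, since the only derivation gives 92 and two other places agree. All of this stands, and it limits the point to a minor one.

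Probabilities can make the gap look larger than it is. If dropouts are independent at 5%, the chance of keeping at least 87 evaluable patients is 34% from 90 and 69% from 92. That contrast depends on a hard cut-off: with 86 as the cut-off the chances are 53% and 82%. Precision for sensitivity depends on the number of ROSC patients, and the chance of at least 35 of them is 47% from 90 and 54% from 92. The verdict does not rely on these figures.

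It can also be said that the study goal in the enrolment sentence need not mean a patient count, because the same part of the protocol lists five scientific goals. That is fair: the link to when enrolment closes is a plausible reading and is not stated in the text.

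Two other defences do not stand. The 90 cannot be the evaluable number, because the sentence speaks of recruiting and the protocol gives the number before dropout as 87. Nor is it marked as approximate, and if it is a rounding, it rounds below the justified number.

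**Conclusion.** The protocol is wrong as written. It gives two recruitment totals, and 90 conflicts with the 92 in the Study Summary, the Study Design paragraph and the Sample Size Calculations. The contradiction can be seen from the text alone and needs no assumption.

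The calculation behind 92 is correct, so the error is confined to the sentence that states 90. That figure exceeds 87 as it stands; the shortfall appears only once the dropout allowance is taken off. Its size rests on the protocol's 5% dropout and 40% ROSC prevalence, and on reading precision as a two-sided 95% half-width. On those terms, following 90 would cost 1.5 evaluable patients against the requirement and miss the precision target by about 0.05 percentage points. Severity is low, but a recruitment target is a figure the trial relies on and should be corrected.

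**What to change.** In the last sentence of Methods, Study population and selection criteria, change 90 to 92. The cost is one number in the text. It needs no patients beyond those already calculated, and no endpoint or analysis changes.

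### Data collection stops at hospital or ICU admission, which conflicts with recording to the end of resuscitation and does not fit in-hospital arrests, so some ROSC may be missed or misclassified

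*Protocol*

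**What the plan says.** The protocol gives two different ends to observation.

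- **Data collection and reporting:** "Data will be collected throughout the intervention up until death or hospital admission or intensive care admission whichever comes first".
- **Methods, Study Design:** "Monitoring of perfusion index will be initiated as soon as possible and recorded until the end of the resuscitation efforts". The same section says of the comparator: "ETCO₂ will be placed as soon as possible and recorded until the end of the resuscitation".

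Three other places bear on how these rules work in practice.

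- **Study Summary, Outcomes:** "Return of spontaneous circulation in a mixed population of out-of-hospital and in-hospital cardiac arrest".
- **Background:** one stated use of prognostication is, "in the prehospital setting, to inform the decision on transport to hospital".
- **Recruitment methods**, on who enters the study: "All subjects that will be treated by the mobile intensive care unit of CHU Saint Pierre during study period will be screened for eligibility".

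The Primary Endpoint section of the protocol's statistical plan averages PI over two minutes and tests each value against ROSC in the next two-minute cycle. It also defines ΔPI from the initial value to the cycle before ROSC or, if there was no ROSC, to the last cycle. The Secondary Endpoints section adds patient-level comparisons based on initial and final PI and ETCO₂. Nothing in the protocol defines hospital admission or says how a patient still being resuscitated at that point is classified.

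**The concern.** The collection rule is tied largely to where the patient is, whereas the primary outcome depends on when the arrest ends. The two can diverge in two groups.

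1. **Out-of-hospital arrests brought in with resuscitation continuing.** The Background treats transport as a decision taken during the arrest, so this situation is foreseen. If admission means arrival, collection stops before the outcome is known, while the Study Design rule says recording goes on.
2. **In-hospital arrests.** For a patient who is already an inpatient, hospital admission came before the arrest. Applied literally, the earliest-event rule closes collection before it opens.

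At stake is the outcome label itself. ΔPI recognises two kinds of patient, those with ROSC and those whose last cycle is used because there was none. A patient cut off mid-arrest fits neither unless someone improvises. If such a patient later regains circulation and is counted as non-ROSC, a high PI looks like a false positive and the observed ROSC rate falls. The same cut-off could also shorten observation for the re-arrest endpoint. No later analysis can recover outcome data that were never collected.

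**Working it through.** **Step 1. The rules side by side.**

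| Patient | Data collection rule | Study Design recording rule | Compatible? |
|---|---|---|---|
| Out-of-hospital, ROSC or death before admission | ends at death or admission | ends with resuscitation | Yes |
| Out-of-hospital, arrives in arrest, admission = arrival | ends on arrival | continues | No |
| Out-of-hospital, arrives in arrest, admission = inpatient admission after emergency care | ends at death, or at admission after ROSC | ends with resuscitation | Yes |
| In-hospital, not yet admitted (e.g. emergency department) | ends at death or admission | ends with resuscitation | Yes, if admission follows the arrest |
| In-hospital, already admitted | hospital admission is already past | ends with resuscitation | Not as worded; only death and ICU admission are usable |

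**Step 2. The plan's own sample size.** Inputs from Sample Size Calculations: sensitivity and specificity 90%, ROSC prevalence 40%, precision 10 points, type I error 0.05 (taken as two-sided), dropout 5%.

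- Patients with ROSC needed: 1.96² × 0.9 × 0.1 / 0.1² = 34.57.
- Total for sensitivity: 34.57 / 0.40 = 86.4, rounded up to 87.
- Total for specificity: 34.57 / 0.60 = 57.6, rounded up to 58, so sensitivity governs.
- With dropout: 87 / 0.95 = 91.6, rounded up to 92.

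Both stated figures, 87 and 92, reproduce and are not in dispute.

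**Step 3. Conditional illustration, patient level.** With 87 patients, 0.40 × 87 = 34.8, so take 35 with ROSC and 52 without. Assume that k of the 35 regain circulation after the cut-off, are counted as non-ROSC, and are missed independently of PI. Each is then PI-negative with probability 0.1. The documents give no value for k.

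Apparent specificity = (52 × 0.9 + k × 0.1) / (52 + k). Observed ROSC rate = (35 − k) / 87.

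| k | Apparent specificity | Observed ROSC rate |
|---|---|---|
| 0 | 46.8/52 = 90.0% | 35/87 = 40% |
| 1 | 46.9/53 = 88.5% | 34/87 = 39% |
| 2 | 47.0/54 = 87.0% | 33/87 = 38% |
| 4 | 47.2/56 = 84.3% | 31/87 = 36% |
| 6 | 47.4/58 = 81.7% | 29/87 = 33% |

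Under the same assumption expected sensitivity is unchanged but less precise. The half-width 1.96 × √(0.09/n) is 9.97 points at n = 34.8, 10.6 at n = 31 and 10.9 at n = 29. The planned size only just reaches 10 points, so there is little slack.

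**Step 4. Per-cycle analysis.** Each two-minute value is judged only against ROSC in the next cycle. A ROSC many cycles later is correctly a negative for the earlier values. Stopping early therefore drops later cycles and can mislabel at most the last recorded one. The table in Step 3 does not describe this analysis.

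**The case against.** The strongest reply is that the rule can be read harmlessly. The Background lists ROSC, surviving to admission and surviving to discharge as successive outcomes, which suggests that admission follows a survived arrest. The collection rule also speaks of the whole intervention. On that reading a patient brought in under resuscitation either dies or regains circulation and is then admitted, and no ROSC is lost. The collection rule would then be the longer of the two windows, and the re-arrest endpoint needs observation after ROSC. For in-hospital arrests, death and ICU admission remain usable end points, and an arrest in an emergency department before admission raises no difficulty.

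Much of this stands. A reader might infer that late ROSC will be recorded as no ROSC, or that the rule cannot be applied to any in-hospital arrest. The protocol supports neither. It states no such coding: the ΔPI wording only selects which PI value to use, and a patient still in arrest at the cut-off could equally be censored, excluded or followed up. Nor do the documents show that transported patients have high PI, and k = 6 would mean 6/35 = 17% of all ROSC falling after the cut-off, for which there is no source.

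The harmless reading is nevertheless only one reading of an undefined term. It does not make the hospital-admission limb fit patients who were already admitted, and screening through the mobile intensive care unit does not remove in-hospital arrests from the stated population.

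**Conclusion.** The point holds as an inconsistency in a stated rule. The end of data collection does not agree with the end of PI and ETCO₂ recording for anyone admitted while still in arrest, and it does not fit patients whose admission preceded the arrest. Whether ROSC is actually lost depends on what hospital admission means. If it means arrival with resuscitation under way, later ROSC may be missed or misclassified, chiefly in ΔPI and the initial- and final-value analyses.

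The size is unknown. The fall in specificity from 90% to between 88.5% and 81.7% rests on four assumptions: the arrival reading, coding as non-ROSC, 1 to 6 affected patients, and loss unrelated to PI. It is an illustration and should not be read as an expected bias, least of all for the per-cycle primary analysis. The change is still worth making, because it corrects something the protocol states and protects the primary outcome at little cost.

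**What to change.** Reconcile the Data collection and reporting section with the Study Design section:

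- Define hospital admission.
- Collect ROSC status until ROSC or the end of resuscitation for that arrest, wherever it occurs.
- Let hospital or ICU admission end collection only once ROSC has occurred.
- Do not use hospital admission as an end point for patients already admitted when they arrest.
- If the study monitor is removed on arrival, take ROSC status from the receiving hospital's record.

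This changes data collection only and leaves care untouched. It costs about one sentence of amendment plus a record check for patients who arrive with resuscitation in progress. That check may involve another hospital, because the protocol does not say that every patient goes to the study centre.
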